4.1. Primary Objective(s) or Main Objective(s)

This study is exploratory in nature and there are no specified hypotheses or performance requirements for the Primary Objectives. All mentions of the intervention in the objectives below refer to the process improvement intervention that will be implemented at the start of Phase II. All mentions of the diagnosis of SND refer to symptomatic SND.

4.1.1. Primary Objective #1

Evaluate the impact of the intervention on the diagnosis of SND.

4.1.1.1. Endpoint Definition

The absolute change in the proportion of subjects diagnosed with SND at pre-specified time points (% = number diagnosed/number enrolled x 100 at time point t where t = 6, 12, and any additional 6-month interval for which there is sufficient follow-up information) and the absolute change in the number of subjects diagnosed with SND per person-year. An SND diagnosis will be determined by the response on the Diagnosis Form on the CRF. If any response under the heading of Sinus Node Dysfunction is selected, the subject will be considered to have been diagnosed with SND. Responses under the heading of Sinus Node Dysfunction include

- Minimally symptomatic SND, with heart rate less than 40 bpm while awake and no evidence of chronotropic incompetence (Class IIb)
- SND, with heart rate less than 40 bpm and no symptom rhythm correlation present (Class IIa)
- Symptomatic bradycardia, brady-tachy syndrome (Class I)
- Symptomatic bradycardia, sinus arrest/pause/exit block (Class I)
- Symptomatic bradycardia, sinus brady (Class I)
- Symptomatic Chronotropic incompetence (Class I)
- Symptomatic SND/bradycardia, drug induced (Class I)
- Symptomatic SND, sinus tachycardia (Class I)
- Syncope, spontaneous or induced in EP study (Class I)
- Syncope of unknown origin with EP findings (Class IIa)

If none of these diagnoses were indicated on the Diagnosis Form on the CRF, the subject will be considered to not have been diagnosed with SND.

4.1.2. Primary Objective #2

Evaluate the impact of the intervention on SND subjects receiving an indicated IPG device.

This document is electronically controlled. Printed copies are considered uncontrolled.

Confidential

4.1.2.1. *Endpoint Definition*

The absolute change in the proportion of subjects receiving indicated therapy at pre-specified time points (% = number receiving IPG/number with SND diagnosis x 100 at time point t where t= 3, 6, and any additional 3-month interval for which there is sufficient follow-up information) and the absolute change in the number of subjects implanted per person-year.

4.2. Secondary Objectives

4.2.1. Secondary Objective #1

Describe the diagnosis and treatment of Phase I subjects.

4.2.1.1. *Endpoint Definition*

The proportion of subjects receiving an SND diagnosis (as described in section 4.1.1.1) and the number of diagnoses that result in indicated therapy at pre-specified time points and the number of subjects diagnosed and implanted per person-year.

4.2.2. Secondary Objective #2

Evaluate the change in the time to diagnosis of SND before and after intervention.

4.2.2.1. *Endpoint Definition*

Time to diagnosis in days (date of diagnosis – date of enrollment); number of visits to diagnosis

4.2.3. Secondary Objective #3

Evaluate the change in the time to receiving an indicated IPG device for SND subjects before and after intervention.

4.2.3.1. *Endpoint Definition*

Time to treatment in days (date of implant – date of diagnosis); number of visits to treatment

This document is electronically controlled. Printed copies are considered uncontrolled.

Confidential

4.2.4. Secondary Objective #4

Evaluate the Caregiver burden between pre-implant and 6 months post-implant.

4.2.4.1. Endpoint Definition

Compare the difference in caregiver burden from pre-implant to 6 months post-implant. The Zarit survey will be used for assessment.

4.2.5. Secondary Objective #5

Evaluate change in quality of life (QOL) and functional status between pre-implant and 6 months post-implant.

4.2.5.1. Endpoint Definition

Compare the difference in QOL and functional status between pre-implant and 6 months post-implant. The composite physical and mental scores from Version 2 of the SF-12 Health Survey will be used to assess QOL.

[REDACTED]

[REDACTED] [REDACTED]

[REDACTED]

[REDACTED]

[REDACTED]

[REDACTED] [REDACTED]

[REDACTED]

This document is electronically controlled. Printed copies are considered uncontrolled.

Confidential

[REDACTED]

[REDACTED]

[REDACTED]

[REDACTED]

[REDACTED]

[REDACTED]

5. Investigation Plan

Study Design Overview

The study may be conducted in countries located in Central and Eastern Europe (CEE), Greater China, India, Latin America, Asia, and Middle East and Africa (MEA). Countries from other geographies may be added in the future. The distribution of centers will be approximately 10 per geography or country and is determined by local evidence needs.

Approximately 1,650 subjects per geography/country, or up to 14,850 subjects worldwide, will be enrolled in the study. An enrollment target of 6 subjects per center per month is desired to make center-specific outcomes more meaningful and reliable in measuring changes in diagnostic rates and patient acceptance of indicated therapy. Centers that enroll faster than others will be allowed to enroll until 20% of the sample size for the geography/country has been reached for a maximum of 330 subjects per site - 110 maximum in Phase I and 220 maximum in Phase II.

All study subjects will be followed until the study exit criteria are met or until official study closure. Study closure is defined as closure of a clinical study that occurs when Medtronic and/or regulatory requirements have been satisfied per the Clinical Investigation Plan and/or by a decision by Medtronic or regulatory authority, whichever occurs first. The expected study duration per geography/country, from first enrollment to last follow-up, is approximately 4.5 years per geography/country.

Subjects will have successfully completed the study if one of the following criteria has been met:

1. Subject does not meet a class I or class II SND indication for pacing therapy
2. Subject meets an indication for pacing but not an SND indication for pacing therapy
3. Subject has met an SND indication for pacing therapy and did not receive a market released pacemaker from the Medtronic family of devices
4. Subject has met an SND indication for pacing therapy but will not be receiving pacing therapy
5. Subject has completed the final scheduled follow-up visit (in Phase II).

This document is electronically controlled. Printed copies are considered uncontrolled.

Confidential

6. Geography/country completion of Phase I follow-up
7. Study closure

The IMPROVE Brady study will not use randomization to divide subjects into treatment groups, but rather will implement a two-phase design. Since the current rates of SND diagnosis and IPG therapy are not known, it is not feasible to construct a study with two simultaneous treatment arms and adequately power the comparison. Thus, the IMPROVE Brady study will have two sequential phases. In the first phase, the control phase, we expect to obtain baseline measurements for key variables including the rate of SND diagnosis and the rate of implantation of an IPG in subjects with an SND diagnosis. Once phase one enrollment is complete for a geographic region, patients will be followed for six months and then will be exited from the study. Physicians at participating centers will then receive an educational intervention and comprehensive disease state management tools on the adoption of ACC/AHA/HRS and ESC indications. In the second phase, the experimental phase, patients will have scheduled follow-up to collect questionnaire data if they are implanted with an IPG manufactured by Medtronic.

Each of the geographies currently participating has differing rates of SND diagnosis and implantation. Early enrollment figures anticipate the accrual of 60 subjects per month per geography, to be obtained through ten or more clinical centers. Given that baseline disease and treatment rates differ by geography, we anticipate that statistical analysis will stratify by geography and thus sample size calculations shall be stratified also. It may also be necessary to look more finely at rates by site within geography. All primary and secondary objectives will be investigated within each geography, in addition to the overall testing of primary and secondary objectives, which will include geography as a covariate.

Baseline IPG Rates

Table 1 shows WHO estimates of new implantation rates per million people (Mond *et al*)

Table 1

Region	Country	Centers	New Implants/Million (2005)
Eastern Europe	Russia	99	101
Asia	China	417	13
	Hongkong	20	157
	South Korea	100	29
	Taiwan	78	119
Southeast Asia	India	417	7
	Singapore	10	91
	Thailand	46	22

This document is electronically controlled. Printed copies are considered uncontrolled.

Confidential

Latin America	Argentina	NA	294
	Chile	50	153
	Panama	5	80
	Uruguay	14	287

The rates in Table 1 are lower than those in developed countries such as Canada (550 implants per million) and the US. The number of new implants in the US in 2009 was 616/million (Greenspon *et al*). Thus, it is estimated that the number of IPGs implanted due to SND would be about 50-70% or 308-431 implants/million (Rodriguez *et al*, P3 Patient Profiling Study Final Report). The implantation rates in other geographies outside of the US are lower, suggesting that current pacing therapies may be underused in bradycardia subjects worldwide.

The current plan is to enroll by site in two phases. The first phase would enroll for 10-12 months and the second phase would be twice as long. If the study plan uses 10 months of Phase I subjects, this will result in roughly 550 subjects per geography. This is based on the anticipated ability to enroll subjects at the rate of 55 subjects per month per geography. The study team anticipates that enrollment timing and rates will vary between the geographies. Phase II is currently planned to enroll subjects for twice as long as Phase I, resulting in roughly 1100 subjects per geography. This is based on the anticipated ability to enroll subjects at the rate of 55 subjects per month per geography. In general the study will start with a 1:2 collection ratio for Phase I and Phase II sample sizes. Twice as many subjects are enrolled in Phase II of the study design so that the study may also examine any temporal drift in the outcomes of interest or subject demographics.

6. Revision from Version 2.0 of the Statistical Analysis Plan

Study closures by Geography Prior to Phase II

This section has been added to this study SAP following the completion of Phase I in all geographies. While the initial investigation plan intended for the study to be conducted in two phases across multiple geographies, only one geography has opted to complete both phases of the study. The geographies that have completed Phase I of the study are CEE, Latin America and South Asia. Only South Asia has proceeded into Phase II of the study with sites in both India and Bangladesh participating in both phases. CEE and Latin America both terminated their participation in IMPROVE Brady after completing Phase I of the study. Accordingly, planned statistical analyses that were going to investigate study objectives within geography or country can no longer be performed. Therefore, for any analysis comparing phases, it will be performed on the South Asia geography only. Analyses by site within the South Asia geography will only include sites enrolling in both Phase I and Phase II.

This document is electronically controlled. Printed copies are considered uncontrolled.

Confidential

7. Determination of Sample Size

Calculations of Phase II Sample Size Adaptation

The planned sample size in Phase II is up to 1100 enrollments. This sample size assumes that, in Phase I, 20% of enrolled subjects obtain an SND diagnosis and that 10% of subjects with an SND diagnosis then go on to receive indicated therapy with an IPG. This sample size also assumes that 10% of enrolled subjects will be lost to follow-up. The sample size in Phase II will be adapted, however, if the results from Phase I within each geography differ from the original assumptions about diagnosis and implant rates. The adaptation is described below.

Summary

Enrolling 500 subjects in Phase I and 1000 subjects with complete follow-up in Phase II powers the study to detect increases in the SND percentage of 9% or greater. The study is also powered to detect an increase in the IPG implant percentage by 15%. This assumes that the Phase I SND percentage is 20% or greater and that the percent of diagnoses does not decrease in Phase II.

Synopsis of Phase II Preliminary Power and Sample Size Calculations

For Phase II, we will outline many different possible scenarios and the sample sizes required for each. Actual Phase II calculations will depend on what is observed in Phase I within each geography.

Section 4.1 Primary objective #1 for SND

The following assumptions are made for all calculations.

Assumptions:

1. 90% power and type I error of 0.05
2. Phase I enrolled 500 subjects with complete follow-up
3. Overall goal is 2:1 sampling for Phase II versus Phase I
4. Calculation via methods in Fleiss JL, Tytun A, Ury HK (1980): A simple approximation for calculating sample sizes for comparing independent proportions. *Biometrics* 36:343–6.

Table 2. Subjects Required to Observe Changes in SND Diagnosis

SND % Phase I	SND % Phase II	Phase II Subjects	Higher SND % Phase II	Phase II Subjects
------------------	-------------------	----------------------	--------------------------	----------------------

This document is electronically controlled. Printed copies are considered uncontrolled.

Confidential

10%	20%	N=405	25%	N=203
20%	30%	N=593	35%	N=279
30%	40%	N=717	45%	N=327
40%	50%	N=778	55%	N=347
45%	55%	N=785	60%	N=346
50%	60%	N=776	65%	N=338
60%	70%	N=711	75%	N=302
70%	80%	N=582	85%	N=237
80%	90%	N=390	95%	N=144

There is clear power to attain the first primary objective with 873 subjects or fewer in Phase II, accounting for 10% attrition.

Section 4.2 Primary objective #2 for IPG implants

Scenario 1 -- Additional assumptions:

1. No change in SND diagnosis between Phase I and Phase II, i.e., the first primary objective is not met.
2. Futility is assumed when more than 1000 subjects with complete follow-up are needed for Phase II. Areas of futility are not included in **Error! Reference source not found.** and **Error! Reference source not found..**

Table 3. For SND diagnosis rates less than 50%

	IPG % Phase I	IPG % Phase II	Phase II Subjects Needed	Accounting for Attrition	CI width for IPG % with Half of Phase II Data
10% SND = 50 SNDs	80%	95%	>1000	>1000	0.06
	85%	100%	856	952	0.03
20% SND = 100 SNDs	5%	20%	769	855	0.18
	10%	25%	1013	1126	0.17
	15%	30%	>1000	>1000	0.16

This document is electronically controlled. Printed copies are considered uncontrolled.

Confidential

	70%	85%	>1000	>1000	0.07
	75%	90%	968	1076	0.07
	80%	95%	717	797	0.06
	85%	100%	428	476	0.03
30% SND = 150 SNDs	5%	20%	513	570	0.18
	10%	25%	676	752	0.17
	15%	30%	814	905	0.16
	20%	35%	929	1033	0.16
	25%	40%	1021	1135	0.15
	30%	45%	>1000	>1000	0.15
	55%	70%	>1000	>1000	0.14
	60%	75%	1004	1116	0.14
	65%	80%	908	1009	0.13
	70%	85%	788	876	0.13
	75%	90%	645	717	0.12
	80%	95%	478	532	0.10
40% SND = 200 SNDs	85%	100%	286	318	0.08
	5%	20%	385	428	0.18
	10%	25%	507	564	0.17
	15%	30%	611	679	0.16
	20%	35%	697	775	0.16
	25%	40%	766	852	0.15
	30%	45%	817	908	0.15
	35%	50%	850	945	0.15
	40%	55%	866	963	0.15
	45%	60%	864	960	0.14

This document is electronically controlled. Printed copies are considered uncontrolled.

Confidential

	50%	65%	845	939	0.14
	55%	70%	808	898	0.14
	60%	75%	753	837	0.14
	65%	80%	681	757	0.13
	70%	85%	591	657	0.13
	75%	90%	484	538	0.12
	80%	95%	359	399	0.10
	85%	100%	214	238	0.08
50% SND = 250 SNDs	5%	20%	308	343	0.18
	10%	25%	406	452	0.17
	15%	30%	489	544	0.16
	20%	35%	558	620	0.16
	25%	40%	613	682	0.15
	30%	45%	653	726	0.15
	35%	50%	680	756	0.15
	40%	55%	693	770	0.15
	45%	60%	691	768	0.14
	50%	65%	676	752	0.14
	55%	70%	646	718	0.14
	60%	75%	603	670	0.14
	65%	80%	545	606	0.13
	70%	85%	473	526	0.13
	75%	90%	387	430	0.12
	80%	95%	287	319	0.10
	85%	100%	172	192	0.08

This document is electronically controlled. Printed copies are considered uncontrolled.

Confidential

Table 4. For SND diagnosis rates greater than 50%

	IPG % Phase I	IPG % Phase II	Phase II Subjects Needed	Accounting for Attrition	CI width for IPG % with Half of Phase II Data
60% SND = 300 SNDs	5%	20%	257	286	0.18
	10%	25%	338	376	0.17
	15%	30%	407	453	0.16
	20%	35%	465	517	0.16
	25%	40%	511	568	0.15
	30%	45%	545	606	0.15
	35%	50%	567	630	0.15
	40%	55%	577	642	0.15
	45%	60%	576	640	0.14
	50%	65%	563	626	0.14
	55%	70%	539	599	0.14
	60%	75%	502	558	0.14
	65%	80%	454	505	0.13
	70%	85%	394	438	0.13
	75%	90%	323	359	0.12
70% SND = 350 SNDs	80%	95%	239	266	0.10
	85%	100%	143	159	0.08
	5%	20%	220	245	0.18
	10%	25%	290	323	0.17
	15%	30%	349	388	0.16
	20%	35%	399	444	0.16
30%	25%	40%	438	487	0.15
	30%	45%	467	519	0.15

This document is electronically controlled. Printed copies are considered uncontrolled.

Confidential

	35%	50%	486	540	0.15
	40%	55%	495	550	0.15
	45%	60%	494	549	0.14
	50%	65%	483	537	0.14
	55%	70%	462	514	0.14
	60%	75%	431	479	0.14
	65%	80%	389	433	0.13
	70%	85%	338	376	0.13
	75%	90%	277	308	0.12
	80%	95%	205	228	0.10
	85%	100%	123	137	0.08
80% SND = 400 SNDs	5%	20%	193	215	0.18
	10%	25%	254	283	0.17
	15%	30%	306	340	0.16
	20%	35%	349	388	0.16
	25%	40%	383	426	0.15
	30%	45%	409	455	0.15
	35%	50%	425	473	0.15
	40%	55%	433	482	0.15
	45%	60%	432	480	0.14
	50%	65%	423	470	0.14
	55%	70%	404	449	0.14
	60%	75%	377	419	0.14
	65%	80%	341	379	0.13
	70%	85%	296	329	0.13
	75%	90%	242	269	0.12

This document is electronically controlled. Printed copies are considered uncontrolled.

Confidential

	80%	95%	180	200	0.10
	85%	100%	107	119	0.08
90% SND = 450 SNDs	5%	20%	171	190	0.18
	10%	25%	226	252	0.17
	15%	30%	272	303	0.16
	20%	35%	310	345	0.16
	25%	40%	341	379	0.15
	30%	45%	363	404	0.15
	35%	50%	378	420	0.15
	40%	55%	385	428	0.15
	45%	60%	384	427	0.14
	50%	65%	376	418	0.14
	55%	70%	359	399	0.14
	60%	75%	335	373	0.14
	65%	80%	303	337	0.13
	70%	85%	263	293	0.13
	75%	90%	215	239	0.12
	80%	95%	160	178	0.10
	85%	100%	96	107	0.08

Additional calculations:

If the Phase II data is divided into two pieces, then there would be, ideally, an equal number of SND diagnoses and number treated with IPG in each piece. The following table describes the width of the confidence intervals around the IPG proportions estimated in Phase II, the width around the point estimate for one half of the Phase II enrollments and the width around the difference in the proportions from the two halves of Phase II.

Table 5. For SND diagnosis rates greater than 50%

IPG % Phase II	Number of SND dx in Phase II	CI width for IPG % with Half of Phase II Data	CI width for Comparison of IPG % Between Two Halves of Phase II
20%	154	0.19	0.26
25%	203	0.18	0.24
30%	245	0.17	0.23
35%	279	0.16	0.22
40%	307	0.16	0.22
45%	327	0.16	0.22
50%	340	0.16	0.21
55%	347	0.15	0.21
60%	346	0.15	0.21
65%	338	0.15	0.20
70%	323	0.15	0.20
75%	302	0.14	0.20
80%	273	0.14	0.19
85%	237	0.14	0.18
90%	194	0.13	0.16
95%	144	0.11	0.13

To compare the SND proportion between these two pieces, we have a confidence interval total width of 12% (absolute range) or less. To compare the IPG proportion between these two pieces, we have a confidence interval total width of 26% (absolute range) or less.

Futility examples

Suppose that the SND percentage is 10% and that less than 85% of those indicated will implant. Assuming 500 patients in Phase I, we will need 2,520 patients in Phase II to see an increase in the implant rate from 10% to 30%. This is an example of a scenario where we may decide not to move forward into Phase II.

This document is electronically controlled. Printed copies are considered uncontrolled.

Confidential

Suppose that the SND percentage is 5% and that 5% of those indicated will implant. Assuming 500 patients in Phase I, we will need 5,440 patients in Phase II to see an increase in the implant rate from 5% to 30%. This is another example of a scenario where we may decide not to move forward into Phase II.

Suppose that the SND percentage is 20% and that 40% of those indicated will implant. Assuming 500 patients in Phase I, we will need more than 10,000 patients in Phase II to see an increase in the implant rate from 40% to 55%. If there are 910 patients in Phase II, this is sufficient to detect an increase in the implant rate from 40% to 60%.

8. Statistical Methods

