1.2 Study Scope

The study may be conducted in countries located in Central and Eastern Europe (CEE), Greater China, India, Latin America, Asia, and Middle East and Africa (MEA). Countries from other geographies may be added in the future. The distribution of centers will be approximately 10 per geography or country and is determined by local evidence needs.

Approximately 1,650 subjects per geography/country, or up to 14,850 subjects worldwide, will be enrolled in the study. An enrollment target of 6 subjects per center per month is desired to make center-specific outcomes more meaningful and reliable in measuring changes in diagnostic rates and patient acceptance of indicated therapy. Centers that enroll faster than others will be allowed to enroll until 20% of the sample size for the geography/country has been reached for a maximum of 330 subjects per site.

All study subjects will be followed until the study exit criteria are met or until official study closure. Study closure is defined as closure of a clinical study that occurs when Medtronic and/or regulatory requirements have been satisfied per the Clinical Investigation Plan and/or by a decision by Medtronic or regulatory authority, whichever occurs first. The expected study duration per geography/country, from first enrollment to last follow-up, is approximately 4.5 years per geography/country.

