11 STATISTICAL METHODS AND DATA ANALYSIS

Medtronic statisticians will conduct all statistical analysis. The sample size package PASS 2008 was used for sample size evaluation. In this study, it is hypothesized that the use of a practice-specific process improvement intervention consisting of education, diagnostic algorithm(s) and documentation tools that advocate and reinforce adherence to consensus treatment guidelines will improve the quality of care for patients with sinus node dysfunction (SND). The two primary endpoints are the impact of the intervention on the diagnosis of subjects

with SND and whether SND indicated subjects receive IPG therapy. In current practice, both of these proportions are unknown for a set of patients meeting the study inclusion criteria. Three principles will guide the statistical analysis outlined below. The first principle is that the sample size calculations will use exact confidence intervals and tests to compare rates and binomial proportions. The second principle of the analysis is that sample size calculations for Phase II (intervention phase) of the study design will depend on the outcomes observed in Phase I (control phase) of the study design. Due to this, the Phase II sample size calculations provided herein are preliminary calculations that will be amended once Phase I data collection is completed. In general the study will start with a 1:2 collection ratio for Phase I and Phase II sample sizes. Twice as many subjects are enrolled in Phase II of the study design so that the study may also examine any temporal drift in the outcomes of interest or subject demographics. The 1:2 collection ratio will also allow for more information to contribute to secondary objectives 3 and 4. The third principle of the analysis is that both the statistical methods and the Phase II sample size calculations will be geography/country specific because the study outcomes are expected to vary by geography/country.

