11.1 Primary Objective(s)

Primary Objective #1

Evaluate the impact of the intervention on the diagnosis of SND.

Endpoint Definition

The absolute change in the proportion of subjects diagnosed with SND at pre-specified time points ($\% = \text{number diagnosed}/\text{number enrolled} \times 100$ at time point t where $t = 6, 12$, and any additional 6-month interval for which there is sufficient follow-up information) and the absolute change in the number of subjects diagnosed with SND per person-year.

Analysis Methods

A. Statistical Methodology

To compare the proportion of subjects with an SND diagnosis pre-intervention (Phase I) to the proportion post-intervention (Phase II), a chi-square test will determine statistical significance. The proportion of subjects diagnosed will be evaluated at multiple time points because the time to diagnosis is expected to vary by geography. Thus, times are pre-specified starting at 6 months and any additional 6-month interval thereafter for which there is sufficient follow-up data available to compare study phases. Proportions calculated at all available time points will be reported. Additionally a Poisson regression will compare the average number of subjects with an SND diagnosis in Phase I and Phase II where the subject time in study is treated as an offset in the model. The above described tests will be performed separately within geography/country as well as overall.

B. Determination of Patients/Data for Analysis

All subjects that are enrolled in the study will be included in the determination of the proportion estimates. The proportion estimates will be calculated based on information from fixed time points at 6 months of follow-up, 12 months of follow-up, and any additional 6-month interval thereafter for which there is sufficient follow-up data available to compare study phases. The number of subjects that obtain a SND diagnosis by pre-specified time point $t= 6, 12, \text{ etc.}$, is included in the numerator and the number of subjects enrolled is included in the denominator.

Sample Size Methods and Assumptions

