For Secondary Objectives 2 and 3 above, the following statistical analysis is proposed. A stratified log-rank test of two Kaplan-Meier curves will determine if there is a significant difference in the time to endpoint before and after intervention. The stratification will occur by geography/country and also by site. Stratified Cox models may also be fit to examine independent variables of interest that may affect SND diagnosis, such as gender and age. Descriptive statistics will be used to characterize the number of visits that occur before an SND diagnosis and between the diagnosis and implant and further will examine number of visits separated by Phase, geography/country, type of enrolling physician, and possibly other baseline characteristics.

B. Determination of Patients/Data for Analysis

The subjects to include in the analysis of secondary objectives 2 and 3 are the same as specified for primary objectives 1 and 2 respectively.

Secondary Objective #4

Evaluate the Caregiver burden between pre-implant and 6 months post-implant

Endpoint Definition

Compare the difference in caregiver burden from pre-implant to 6 months post-implant

Analysis Methods**A. Statistical Methodology**

Descriptive statistics will be used to summarize the difference in caregiver burden between pre-implant and 6 months post-implant.

B. Determination of Patients/Data for Analysis

Subjects in Phase II who opt to receive an indicated therapy and are implanted with a market released pacemaker from the Medtronic family of devices will be followed from implant to 6 months post-implant. The primary caregiver of these subjects will be asked to complete a questionnaire that assesses caregiver burden at the time of implant and 6 months post-implant.

Secondary Objective #5

Evaluate change in Quality of Life (QOL) and functional status between pre-implant and 6 months post-implant.

Endpoint Definition

Compare the difference in QOL and functional status between pre-implant and 6 months post-implant.

Analysis Methods**A. Statistical Methodology**

Descriptive statistics will be used to summarize the difference in QOL and functional status between pre-implant and 6 months post-implant.

B. Determination of Patients/Data for Analysis

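### SAP section 6 gives a reason for dropping within-country analysis that does not apply to South Asia, and the visible phase comparisons pool India and Bangladesh with no country or site term

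*SAP*

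**What the plan says.** **Protocol.** Section 11 states as a principle: "both the statistical methods and the Phase II sample size calculations will be geography/country specific because the study outcomes are expected to vary by geography/country". For each primary objective, section 11.1 then says: "The above described tests will be performed separately within geography/country as well as overall". For the two time-to-event objectives, section 11.2 specifies a stratified log-rank test: "The stratification will occur by geography/country and also by site". Section 1.2 lists the study areas as "Central and Eastern Europe (CEE), Greater China, India, Latin America, Asia, and Middle East and Africa (MEA"), so India is a named unit separate from Asia. Bangladesh is not named.

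**SAP section 6**, added after Phase I ended, says that CEE and Latin America terminated after Phase I. It adds: "Only South Asia has proceeded into Phase II of the study with sites in both India and Bangladesh participating in both phases". From the departures it concludes that "planned statistical analyses that were going to investigate study objectives within geography or country can no longer be performed", and it limits every phase comparison to South Asia. By-site analyses are restricted to sites that enrolled in both phases.

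**SAP section 8.5.** The chi-square and Poisson analyses (8.5.1.1), the Fisher and Poisson analyses (8.5.2.1) and the two log-rank tests (8.5.4.1, 8.5.5.1) are each run on South Asia. None shows a country or site term in the visible text. Blocks are redacted in 8.5.1.1 and 8.5.4.1; no redaction is marked in the methods of 8.5.2.1 or 8.5.5.1.

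**The concern.** The departure of two regions makes phase comparisons impossible in those regions. It has no bearing on a country that contributed to both phases, and section 6 says that two countries did. A protocol-planned level of analysis is therefore given up for a reason that does not cover the only data still to be compared.

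This matters because the comparison is before-after and not randomised. Anything that shifts the make-up of the sample between phases can look like an intervention effect. Country is an obvious candidate, since the protocol itself expects outcomes to differ along this line. Enrolment caps are set per site, and the documents set no quota per country, so nothing fixes the India-to-Bangladesh ratio across phases. A shift could create a difference where neither country changed, or hide one where both did.

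**Working it through.** **1. The two statements in SAP section 6.** Premise: CEE and Latin America have no Phase II. Conclusion: analysis within geography or country is no longer possible. Counter-fact in the same section: "sites in both India and Bangladesh participating in both phases". The premise supports the conclusion for CEE and Latin America only. Section 6 itself goes on to plan a phase comparison within one geography, so its sentence cannot be literally correct.

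**2. Whether anything else visible adjusts for country.** SAP section 5 planned geography as a covariate in the overall tests; with only South Asia left it is constant. The interrupted time series model in SAP 8.2.1 contains time, phase and a follow-up offset, but no country or site. The both-phase site restriction applies to by-site analyses only, while the primary objective 1 set is all enrolled subjects.

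**3. The plan's own yardstick.** SAP 8.5.1.2: 500 and 1000 subjects, 20% v 28%, alpha 0.05 (taken as two-sided), power 0.90.
- Pooled proportion = (500×0.20 + 1000×0.28)/1500 = 0.2533
- Null SE = √(0.2533×0.7467×(1/500 + 1/1000)) = 0.0238
- Alternative SE = √(0.20×0.80/500 + 0.28×0.72/1000) = 0.0228
- Power = Φ((0.08 − 1.96×0.0238)/0.0228) = 92.8%

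The smallest increase detectable at 90% power is 7.6 points, so the stated 8 points is reproduced. With a Phase I rate of 20%, an observed rise of about 4.5 points already gives p<0.05.

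**4. Size of a country-mix bias, primary objective 1.** Country rates and shares are assumptions, because the documents give none. Call the countries A and B, with no intervention effect in either.
- False difference = (A's share in Phase II − A's share in Phase I) × (A's rate − B's rate)
- z = false difference / √(p̄(1−p̄)(1/550 + 1/1100)), where p̄ is the rate over both phases
- Rejection probability = Φ(z − 1.96) + Φ(−z − 1.96)

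| Rates A / B | A's share, Phase I to II | Pooled rates, I / II | False difference | Rejection |
|---|---|---|---|---|
| 20% / 30% | 70% to 60% | 23% / 24% | 1 point | 7% |
| 15% / 25% | 70% to 60% | 18% / 19% | 1 point | 8% |
| 15% / 25% | 70% to 50% | 18% / 20% | 2 points | 16% |
| 15% / 35% | 70% to 60% | 21% / 23% | 2 points | 15% |
| 15% / 35% | 70% to 50% | 21% / 25% | 4 points | 44% |
| 15% / 35% | 90% to 70% | 17% / 21% | 4 points | 49% |

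For the 44% row: p̄ = (550×0.21 + 1100×0.25)/1650 = 0.2367, SE = 0.0222, z = 0.04/0.0222 = 1.80. Swapping the direction of the share change reverses the sign of the bias.

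**5. Effect of stratifying.** In simulations at 500/1000 (40,000 runs per scenario, no true effect), with similar assumed rates and shares and some more extreme ones, a country-stratified Cochran-Mantel-Haenszel (CMH) test rejected 4.8% to 5.2% of the time throughout. The pooled test rejected 41.1% of the time for rates of 30% and 10% with the first country's share rising from 50% to 70%. With equal rates or an unchanged mix, the pooled test was not biased.

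**6. What separate country tests could show.** Power for 20% v 28% by a country's share of 500/1000: 80% share, 86.2%; 50% share, 66.7%; 20% share, 31.6%.

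**The case against.** Several points on the other side stand.

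- **Meaning of geography/country.** The protocol mostly uses it as one label for an enrolment unit, with about 10 centres and 1,650 subjects each. On that reading South Asia is the unit, and the SAP does test within it. A reader might infer that the protocol requires a separate Bangladesh test. The documents do not support that, since Bangladesh is not named in the protocol. The case is stronger for India, and SAP section 6 itself names country as a level of the planned analyses.
- **Loose wording.** The disputed sentence may only mean that the multi-geography programme is over. That is plausible, but an analyst following it would still run no country analysis.
- **Redaction.** A reader might infer that the tests are certainly unadjusted. Hidden text in 8.5.1.1 and 8.5.4.1 could hold a site or country adjustment, so the claim extends only to the visible text.
- **Existing safeguards.** By-site analyses limited to both-phase sites would remove country mix if each site lies in one country. Site caps of 110 and 220 follow the 1:2 phase ratio and restrain shifts. Both help, but neither is visibly tied to the primary tests.
- **Exploratory status.** SAP 4.1 sets no hypotheses for the primary objectives, so the rejection rates carry less weight. The bias in the estimate is unaffected.

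**Conclusion.** The concern holds in a limited form. The reason given in SAP section 6 does not rule out a within-country phase comparison in South Asia, and the visible phase comparisons omit the country and site structure that the protocol had planned.

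It would go too far to say that the South Asia result is biased. Bias needs both a rate difference between the countries and a change in their shares, and the documents show neither. The 1 to 4 points and 7% to 49% are conditional on assumed 10- to 20-point gaps in each, at 550/1100, for primary objective 1 only. Every result of 44% or more needs both gaps at 20 points; with both at 10 points, rejection is 7% to 8%, close to nominal. Four points would be half the planned 8-point effect. The same mechanism applies to implant rates under primary objective 2, but its size was not worked out.

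This should be changed: the risk is of unknown size, but the protection costs little.

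**What to change.** 1. Reword SAP section 6 so that it excludes phase comparisons only in CEE and Latin America.
2. Stratify the South Asia phase comparisons by country or site: CMH for the two sets of proportions, a country term in the Poisson models, and a stratified log-rank test for secondary objectives 2 and 3. If redacted text already does this, say so in section 6.
3. Report the phase difference with a confidence interval for India and for Bangladesh, labelled as descriptive estimates and not as separate powered tests.

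The cost is SAP wording and one stratification variable, which follows from the enrolling site. The downside is that the interval for the smaller country will be wide, as the 31.6% power at a 20% share indicates.
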